Study A. We will use the pilot RCT ($n = 80$) to assess MACS acceptability/ feasibility and its preliminary effectiveness relative to a control condition. Randomization will be used to help ensure balance among treatment conditions. We will stratify by diagnosis (schizophrenia/schizopreniform vs schizoaffective) and by gender (male vs female). We will conduct randomization using a computer generated list via REDCap held by a staff person no otherwise affiliated with the study. We will review patient acceptability/ satisfaction ratings and ease of use of mobile devices as measured by the CSQ-8 and patient qualitative interviews. These data will inform further refinements of the MACS app that will be used in future research.

Study B. We also will conduct 30-minute individual interviews of clinical stakeholders ($n = 20$). Interviews will be led by members of the investigator team and a study research assistant (RA) listening to the conversation and taking notes. Interview agendas will be developed so that participants will receive similar types of questions, as well as those that may be specific to their job responsibilities (e.g., clinician vs administrator).

C3. Specific Procedures or Treatments

MACS Protocol. We will use an established mobile software service (ilumivu.com) which provides a secure platform (Android or Apple IOS compatible) that can be programmed to administer the MACS app. It does not require a high degree of IT support and allows for tailoring of content without the need for trained programmers. Further, we chose a mobile app that works with most smartphones, is easy to download/install, and runs largely autonomously. Because we are using a flexible software platform to deliver our mobile intervention and not a static app specifically designed for this project, we have flexibility to make changes to the content of the app during the project in an iterative fashion based on what we learn from the data being collected. In addition, future implementation of the app can take advantages of ongoing improvements and updates to the platform that will be used in future iterations of our app-based interventions that would be proposed for a next step full-scale RCT if this project is successful.

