Clinical Outcomes and Other Measures. In addition to target mechanisms, we will assess clinical outcomes including: a) symptom severity (primary outcome), b) functioning, and c) re-hospitalization rates. a) We will use the BPRS,⁵⁶ a well-established interview measure of overall psychiatric symptom severity, including positive/negative psychotic symptoms, as well as mood symptoms and suicidality; b) the WHODAS-2^{39,40}, which is a brief self-report measure of functional impairment; and c) rehospitalizations obtained from the THI-4⁵⁰ as described above (and cross-checked with patients' medical records). In addition, the THI-4 will also be used to quantify overall treatment utilization, including the type and amount of mental health treatment received over follow-up (medications, psychosocial, hospitalizations, pharmacotherapy visits, ER visits, crisis calls, support groups). We also will administer the AUDIT/DUDIT, which measure alcohol/drug use and severity^{42,58,64}. The MMSE⁶³ will be used to assess cognitive functioning at baseline in order to describe patients' baseline characteristics and to examine this variable as a potential predictor of treatment response in our analyses. The AMBAS⁶⁵ is a brief self-report measure of medication beliefs. Acceptability/satisfaction with the mobile apps will be assessed using an adapted version of the CSQ-8⁵⁷ at the end of the study. Finally, participants will complete an end-of-treatment interview in which they will be asked what they liked and did not like about the app and study participation.

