We will use effect size changes to describe differences between groups over the time points on target mechanisms (adherence and coping), primary outcomes (overall symptom severity), and secondary outcomes (functioning, rehospitalization rates). We will calculate 95% confidence intervals (CIs) and clinical significance statistics (e.g., NNT). Because CIs will likely be large, these analyses may not permit definitive conclusions. Given the limitations and goals of pilot studies, we hope to build our case for future research by focusing primarily on the feasibility/acceptability of MACS and of the randomized design and the clinical significance of effects compared to our mobile attention control. Some parameters estimated in the pilot study (e.g., stability of outcome measures across time) may be helpful for informing estimates for a large scale, adequately powered RCT. Secondarily and consistent with analyses we would conduct in a future full-scale RCT, we will generate multilevel models to examine whether treatment condition, time, and the treatment condition X time interaction predicts change in outcomes (symptoms, functioning, re-hospitalization) and proposed mechanisms. Generalized estimating equations will be constructed to examine differences in rehospitalization rates over time. We will assess whether the groups differ on covariates at baseline (e.g., demographics) and, if so, include them in the statistical models. Given the smaller sample size, we will examine changes in mediators over time across conditions and correlations between mediators and outcomes, which are pre-requisites for formal mediation. We also will examine outcome predictors (e.g., baseline adherence) to identify possible moderators to test in future studies

Qualitative interviews will be recorded and the interviewer will keep notes of the conversation. The MPIs will develop an initial codebook with deductive codes. Then inductive codes capturing emergent themes will arise from team-level review of interviews. Once codes are developed, the research team will independently code remaining transcripts; 20% of transcripts will be double coded and reviewed to ensure inter-rater reliability. The MPIs will perform thematic analysis in which the passages assigned to codes will be read in aggregate to identify key themes.

C5. Videoconferencing

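### The secondary models choose covariates on chance baseline differences and state neither conditioning on baseline nor adjustment for the strata; the cost is precision and prespecification, with no bias shown

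*Combined protocol and SAP*

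**What the plan says.** Section C4 (Data Analysis) puts descriptive effect sizes and 95% CIs first. The models follow: "Secondarily and consistent with analyses we would conduct in a future full-scale RCT, we will generate multilevel models". Their stated purpose is to examine whether "treatment condition, time, and the treatment condition X time interaction predicts change in outcomes". For readmissions, "Generalized estimating equations will be constructed to examine differences in rehospitalization rates over time"; neither link nor covariates are given.

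The one sentence on covariates in these models is "We will assess whether the groups differ on covariates at baseline (e.g., demographics) and, if so, include them in the statistical models". It names no test, threshold or list beyond the example of demographics.

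Other baseline variables appear only in exploratory roles. C4 says "We also will examine outcome predictors (e.g., baseline adherence) to identify possible moderators to test in future studies". The section on clinical outcomes and other measures collects the MMSE partly "to examine this variable as a potential predictor of treatment response in our analyses". Neither sentence makes these variables adjustment terms.

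Section C2 says "We will stratify by diagnosis (schizophrenia/schizopreniform vs schizoaffective) and by gender (male vs female"). No section says that these factors enter a model. Table 1 schedules the BPRS, WHODAS-2, MACS-II and Brief COPE at baseline and at months 1, 2 and 4, but MEMS only at months 1, 2 and 4.

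**The concern.** In a randomised trial, a baseline difference between arms arises by chance. A rule triggered by such differences says nothing about whether a covariate predicts outcome, which is what decides whether adjusting for it helps. It also leaves the final model open until the data are seen.

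Meanwhile the plan does not mention the covariates with the best prior claim: the baseline value of each outcome and the two stratification factors. With 80 patients, and a plan that itself warns "Because CIs will likely be large, these analyses may not permit definitive conclusions", precision available from data already collected is worth having. At stake are the width of the secondary intervals and whether the model can be known in advance.

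**Working it through.** The plan gives no power, SD, correlation or allocation ratio, so it has no figure of its own to reproduce. **Inputs from the plan:** 80 patients; visits at baseline and months 1, 2 and 4; 95% CIs. **Assumptions:** 40 per arm; outcome SD 1; equal correlation r between any two visits; complete follow-up unless stated.

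**1. Change contrast against conditioning on baseline (BPRS-type outcomes, month 4, categorical time).**
- Unconstrained condition by time: SE = √(2/40) × √(2(1−r)).
- Conditioning on baseline: SE = √(2/40) × √(1−r²).
- Variance ratio = 2/(1+r); narrowing = 1 − √((1+r)/2); equivalent N = 80(1+r)/2.
- Half-width = 1.991 × SE (t, 78 df).

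| r | SE, change | SE, conditioned | Half-widths (SD) | Narrowing | Equivalent N |
|---|---|---|---|---|---|
| 0.3 | 0.265 | 0.213 | 0.527 vs 0.425 | 19.4% | 52 |
| 0.5 | 0.224 | 0.194 | 0.445 vs 0.386 | 13.4% | 60 |
| 0.7 | 0.173 | 0.160 | 0.345 vs 0.318 | 7.8% | 68 |
| 0.8 | 0.141 | 0.134 | 0.282 vs 0.267 | 5.1% | 72 |

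Equivalent N is the number of patients with which the conditioned model matches the 80-patient change contrast. With linear time (generalised least squares, visits 0, 1, 2, 4, baseline as covariate), the narrowing is 18.0, 11.6, 5.6 and 2.8%. With categorical time, a model that constrains the arms to a common baseline mean gives the same gain as in the table. If the condition main effect is kept in it, the gain is 0%.

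**2. What the imbalance rule does to that contrast.** A covariate entered as a main effect shifts all of a patient's visits equally, so it cancels from change over time. With complete data, estimates with and without the flagged covariates agreed to rounding error under both time codings. With 20–30% dropout the estimate moved by a median of about 0.01 SE (largest 0.30) and the SE by less than 0.3%. The rule therefore contributes almost nothing to the loss in step 1.

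**3. How often the rule would trigger.** At an assumed 5% test, the chance of at least one flag among k independent covariates is 1 − 0.95^k:
- k = 4 (demographics): 1 − 0.95⁴ = 18.5%.
- k = 8 (adding MMSE, AMBAS, AUDIT and DUDIT): 1 − 0.95⁸ = 33.7%.

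If the covariates correlate at 0.3–0.5, these fall to 16–17% and 25–30%.

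**4. Outcomes with no baseline value (MEMS).** Nothing cancels here. In simulation (80 patients, one follow-up visit, eight candidate covariates explaining 0–20% of variance), a flagged covariate moved the estimate by a median 0.19–0.39 SE. Coverage under the rule was 94.6–96.1%. Its half-width was 0.448–0.455 SD, against 0.443–0.448 unadjusted, so the rule bought no precision. In a separate simulation with blocks of four, adding the strata lowered the mean SE from 0.223 to 0.218, 0.212 or 0.199 when they explained an assumed 5, 10 or 20% of variance.

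**5. Rehospitalization.** The link is not stated; suppose it is logistic. Take control risk 20–40%, a marginal odds ratio of 0.50 and stratum odds ratios of 1.5–3. Adding strata then **raises** the SE of the conditional log odds ratio: by about 0.3–3.5% with one stratum factor and 0.5–6.6% with two. The conditional odds ratio becomes 0.46–0.50. Only an effect standardised back to the marginal scale can gain precision.

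**The case against.** The strongest reply has four parts.

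- **The sentence on baseline differences does little harm.** This stands. Step 2 shows it is inert for condition by time with complete follow-up, and the 3–19% belongs to a separate gap: C4 does not say how baseline enters. C4 also does not fix the parameterisation. The change contrast is the natural reading, given that the models predict change and the BPRS is measured at all four visits, but it is a reading.
- **The models are secondary in a feasibility pilot, and the plan already concedes wide intervals.** This stands and sets the priority. It does not remove the case for fixing the covariates, since that needs no extra data. At r = 0.8 the half-width changes by only about 0.01 SD; at r = 0.3, by about 0.10 SD.
- **Assessing whether groups differ need not mean a 5% test.** Agreed. The flagging rates are illustrative, and the absence of a criterion is itself part of the point.
- **Some baseline values may not exist.** This stands. BARS asks about the past month's doses of the primary oral drug, while eligibility requires an oral prescription only at discharge. Baseline BARS may be undefined for some patients. So may appointment adherence on the THI-4, if no appointments were scheduled.

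**Conclusion.** The point holds at low to moderate priority. The only covariate rule selects on chance, and conditioning on baseline and adjusting for strata are unstated. On the change-contrast reading, conditioning on baseline would narrow the month-4 interval by 5–19% (categorical time) or 3–18% (linear time) for r from 0.8 down to 0.3. This rests on an assumed r, equal correlations, 1:1 allocation and complete follow-up. For MEMS, the cost is a model that depends on the data.

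A reader might infer three stronger things that the documents do not support:

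- **That the treatment estimate is biased.** Simulation of imbalance-triggered adjustment put the mean estimate within 0.002 SD of the truth. No bias is shown provided covariates are chosen from baseline data alone, though without a list or threshold the plan does not itself rule out a later choice.
- **That the rehospitalization GEE loses precision.** None is shown, and for a conditional odds ratio the SE moves the other way.
- **That a later trial would inherit the rule.** C4 calls the models consistent with those of a full-scale trial, but does not say that this covariate rule would be reused.

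**What to change.** Replace the covariate sentence in C4 with a fixed set:

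- **BPRS, WHODAS-2, MACS-II, Brief COPE:** model months 1, 2 and 4 with the baseline value, diagnosis stratum as randomised, gender, condition, time and condition by time. State the time coding. Report the adjusted between-arm difference and 95% CI at each visit, because the interaction alone no longer carries the whole effect. A constrained-baseline model is an alternative if it omits the condition main effect.
- **MEMS:** adjust for the strata. Add baseline BARS only with a stated rule, such as a missing indicator, for patients with no oral medication in the past month.
- **BARS and THI-4 appointment adherence as outcomes:** apply the same kind of rule where the baseline value is undefined.
- **Rehospitalization GEE:** state the link, include the strata and report a standardised (marginal) effect, claiming no gain for the conditional odds ratio.
- **Everything else:** show baseline balance descriptively and keep imbalance-chosen covariates for sensitivity analysis. Report the model-based differences alongside the planned descriptive effect sizes.

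Before the diagnosis factor is used, reconcile C2 with the inclusion criteria in section 3A. The criteria admit mood disorder with psychotic features, which neither diagnosis stratum in C2 names.

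The cost is one rewritten paragraph in C4 and one clarifying sentence in C2. No new data are needed, since every measure named is in Table 1. Fixed effects rise from 4 to 7 with linear time (adding baseline, diagnosis and gender), or from 8 (4 visits × 2 arms) to 9 (3 visits × 2 arms, plus 3) with categorical time. A third diagnosis stratum would add one more.

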The current project proposes to examine the feasibility, acceptability, and potential effectiveness of our novel response-adaptive app intervention, Mobile After-Care Support (MACS), to improve treatment adherence and self-coping in psychosis following hospitalization, in preparation for a future full-scale clinical trial. We propose to enroll hospitalized patients with schizophrenia spectrum disorders prior to discharge and provide them with the MACS app to use during the first 4 months post-discharge to improve adherence to oral psychotropic medications, appointment attendance, and active self-coping with illness. We will conduct a pilot randomized controlled trial (RCT) of MACS to assess its impact on outcomes of interest relative to an attention-matched control condition. We also will conduct qualitative interviews with clinician stakeholders.

Aim 1: Conduct a pilot RCT (n = 80) of MACS vs mobile app attention control. We will assess: a) acceptability/satisfaction with the mobile app; b) feasibility of the RCT design (e.g., recruitment, randomization, assessments); c) whether the mobile app improves our proposed target mechanisms of increased illness self-coping and treatment adherence; d) whether our mobile app improves primary (symptom severity) and secondary (functioning, rehospitalization) outcomes; and e) whether changes in our adherence and coping target mechanisms predict changes in clinical outcomes.

Aim 2: Conduct 30-minute, individual qualitative interviews with 20 clinical stakeholders (including support staff, clinicians, and administrators) at mental health hospital and outpatient treatment centers in the

RI area. Stakeholder interview agendas will assess: a) perceived barriers to patients' medication/appointment adherence, b) use of mobile devices to support aftercare, c) potential self-management strategies to improve patients' coping, d) challenges patients face upon return to the community post-discharge, e) challenges faced by clinicians/organizations treating this population, and f) preferences regarding the flow of information collected via EMA and what data would be most useful.

B. Background

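### C4 looks for possible moderators among outcome predictors and specifies no baseline variable by condition term, so prognostic variables could be put forward as candidate moderators

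*Combined protocol and SAP*

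**What the plan says.** The last sentence of the quantitative part of C4 (Data Analysis) reads: "We also will examine outcome predictors (e.g., baseline adherence) to identify possible moderators to test in future studies". The method named is a search for predictors of outcome, and the product named is a set of candidate moderators.

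The outcome model is described earlier in the same section: "we will generate multilevel models to examine whether treatment condition, time, and the treatment condition X time interaction predicts change in outcomes". Its terms are condition, time and their interaction. Baseline covariates enter only if the groups differ on them at baseline. Neither C4 nor any other section specifies a product of a baseline variable with condition, or separate slopes by arm.

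Under Clinical Outcomes and Other Measures, the MMSE is collected at baseline partly "to examine this variable as a potential predictor of treatment response in our analyses". The text does not say whether this means overall outcome or a difference in benefit between arms.

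C4 is open about the limits of the pilot: "Because CIs will likely be large, these analyses may not permit definitive conclusions".

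**The concern.** A prognostic variable shifts the outcome by the same amount in both arms. A moderator changes the difference between arms, so its evidence lies in a variable by condition term or, equivalently, in the difference between the two arms' slopes. A search for outcome predictors without that term estimates something else.

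Candidate moderators are one of the things C4 says the pilot will hand on to later studies. If the list is built from outcome predictors, it could be filled with variables that forecast outcome well but say nothing about who gains more from MACS. A larger sample would not cure this, because a prognostic variable would then be flagged more reliably still. The caveat in C4 about wide intervals concerns precision, which is a different matter.

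**Working it through.** **Inputs from the documents.** Sample size: "Conduct a pilot RCT (n = 80) of MACS vs mobile app attention control". Allocation: "Randomization will be used to help ensure balance among treatment conditions", with no ratio stated. Confidence level: 95% intervals in C4, with no alpha stated. The documents give no power, effect size, SD or dropout figure, so there is no planned figure to reproduce.

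**Assumptions (mine).** 1:1 allocation (40 per arm), two-sided alpha 0.05, residual SD 1, baseline variable scaled to SD 1, treatment effect 0.3 SD, one follow-up outcome per patient. All slopes below are illustrative.

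**Model.** Outcome = 0.3 × arm + slope (by arm) × variable + error. Two tests are compared:

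- Main-effect screen: the coefficient of the variable, adjusted for arm. With equal arms it estimates the average of the two slopes, with SE about 1/√N.
- Interaction test: the coefficient of variable × arm. It estimates the difference between the slopes, with SE about 2/√N.

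**Closed-form check at N = 80.**

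- Prognostic slope 0.4: 0.4 ÷ (1/√80) = 0.4 ÷ 0.112 = 3.58, so the chance of a flag is about Φ(3.58 − 1.96) = Φ(1.62) ≈ 0.95.
- Slope difference 0.6: 0.6 ÷ (2/√80) = 0.6 ÷ 0.224 = 2.68, so Φ(2.68 − 1.96) = Φ(0.72) ≈ 0.77.

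Simulation with t-tests and a random baseline variable gives slightly lower values and is used below.

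**Share of simulated trials flagged, N = 80 (at least 10,000 trials per row).**

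| Pattern (slopes in the two arms) | Average slope | Difference | Main-effect screen | Interaction test |
|---|---|---|---|---|
| Prognostic only, 0.4 / 0.4 | 0.4 | 0 | 93% | 5% |
| Prognostic only, 0.25 / 0.25 | 0.25 | 0 | 59% | 5% |
| Crossover moderator, −0.3 / +0.3 | 0 | 0.6 | 6% | 73% |
| One-arm moderator, 0 / 0.6 | 0.3 | 0.6 | 70% | 73% |
| One-arm moderator, 0 / 0.5 | 0.25 | 0.5 | 56% | 57% |
| One-arm moderator, 0 / 0.3 | 0.15 | 0.3 | 26% | 26% |
| Moderator with prognostic slope, 0.1 / 0.7 | 0.4 | 0.6 | 90% | 73% |

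The second and fifth rows are the most telling. Both have an average slope of 0.25; one variable moderates and the other does not. The main-effect screen flags them at nearly the same rate (59% and 56%). The interaction test separates them (5% and 57%).

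**With an assumed 20% loss (N = 64).** A prognostic slope of 0.3 is flagged by the main effect in 64% of trials (73% at N = 80) and by the interaction in 5%. A crossover moderator with slope difference 0.5 gives 6% against 47% (6% against 58% at N = 80). A one-arm moderator with difference 0.5 gives 46% against 48%. The pattern is unchanged.

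**Precision of the interaction.** The 95% half-width is 1.96 × 2/√80 = 0.44 outcome SD per SD of the variable, and 1.96 × 2/√64 = 0.49 after 20% loss. The slope difference detectable with 80% power is (1.96 + 0.84) × 2/√80 ≈ 0.63, or 0.70 at N = 64.

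**The case against.** The best defence is that C4 never says main effect. It names no model for this step, and the outcome models beside it already contain condition, so the team may intend interactions. That stands as a limit on the claim. The main-effect reading is an inference from the wording and from the absence of any variable by condition term. If interactions are intended, the plan still needs to say so.

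Three stronger readings are tempting, and the documents do not support them.

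- **That the screen misses true moderators in general.** It fails outright when the two slopes cancel. A one-arm moderator, or one with a prognostic slope as well, is flagged about as often as by the interaction test or more often. Nothing in the protocol suggests that baseline adherence would show an exact crossover.
- **That the wrong variables would be carried into the full trial.** C4 offers candidates to be tested in future studies. Nothing says they would set eligibility, stratification, sample size or a primary analysis.
- **That the MMSE sentence repeats the error.** A predictor of treatment response can mean a variable that identifies who benefits, which is moderation. The phrase is ambiguous and proves nothing either way.

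It is also fair to say that the interaction test is weak here. At a slope difference of 0.3 in one arm it finds the moderator only 26% of the time, no better than the main-effect screen. Moderators are not among the items listed under Aim 1, and C4 gives priority to feasibility and acceptability.

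**Conclusion.** The concern holds in limited form. C4 goes from outcome predictors to possible moderators with no term that measures moderation. On the natural reading, the screen cannot tell a prognostic variable from a moderator: under the assumed values, a non-moderator with slope 0.4 is flagged about 93% of the time, against about 5% by the interaction. Missed moderators are a problem for crossover-type patterns (about 6% against 73%) and not for one-arm moderators (about 70% against 73%).

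The consequence is that prognostic variables could be put forward as candidate moderators. No primary, secondary or feasibility conclusion depends on this sentence, so the severity is minor. The percentages rest on assumed slopes, 1:1 allocation, alpha 0.05, a single follow-up outcome and, for the headline figures, no dropout. The mismatch between the quantity sought and the quantity estimated does not depend on those values.

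**What to change.** Amend the sentence in C4 along these lines:

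- Name a short list in advance: baseline adherence and MMSE, which the protocol already mentions, and diagnosis stratum. State the measure for each. In Table 1, MEMS starts at month 1, so baseline medication adherence would come from the BARS. The diagnosis levels also need defining, since the two strata in C2 do not cover the mood disorders with psychotic features that the inclusion criteria admit.
- For each variable, add variable × condition (and × time) to the outcome model. Report the interaction estimate with its 95% CI and the slope in each arm, labelled exploratory.
- Report main effects separately, as prognostic predictors.
- Say in the same place whether the MMSE is to be examined as a predictor of outcome, a moderator, or both.

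The cost is a few lines of text and a few model terms, using baseline data already scheduled. The drawback is imprecision: a half-width of about 0.44 SD at 80 patients, wider with dropout. Candidates should therefore be described by estimate and interval, not selected by significance or put in a firm rank order.
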